## 3.10 Withdrawals, Dropouts, Loss to Follow-up

Subjects who are withdrawn or discontinue from the study will not be replaced.

#### 3.11 Missing, Unused, and Spurious Data

Statistical methods for addressing missing data for the analyses of the primary and secondary efficacy endpoints are described in Section 4.3.

Rules for imputation of missing dates for onset of AEs and start of concomitant medications are included in Appendix D of this SAP. Unless otherwise specified, missing dates for onset of AEs and start of concomitant medications will be handled according to those imputation rules.

In the event that incorrect data are discovered after database lock, the impact of such incorrect data will be assessed and a determination will be made as to whether the data need to be corrected in the database (and subsequently in the analysis). In cases where it is decided that the data need to be corrected, the decision will be documented, and the documentation will be saved in the Trial Master File.

All available data will be included in data listings.

#### 3.12 Visit Windows

In general, the nominal visit will be used for the safety and efficacy data summaries and analyses.

During the COVID-19 pandemic, if a subject's DXA and/or QCT assessment cannot be performed during the protocol specified visit windows, the site will contact the study Medical Monitor and the subject will be allowed to make up the visits within an allowed time period. The allowable time period for collection of DXA and QCT assessments are shown in Table 3, where the ideal visit date is defined as the date that represents the ideal number of days from the date of first dose of study drug to the nominal visit.

Table 3:         Allowable Time Period for Collection of DXA and QCT Assessment
---

Visit	Ideal Visit Day	BMD or vBMD Assessment
Month 3	90	Up to 30 days after ideal visit day
Month 6	180	Up to 90 days after ideal visit day
Month 12	360	Up to 30 days after ideal visit day

Due to the expanded time periods for collection of efficacy assessments, analysis visit windows are defined below for the analyses of BMD, vBMD, and serum markers of bone metabolism (PINP and CTX) data to determine the assessment that will be used for a given study visit.

Table 4: Analysis V	Visit Windows	for BMD.	, vBMD, s	s-PINP and	I s-CTX.
---------------------	---------------	----------	-----------	------------	----------

Visit / Month	Allowable days from first dose of study drug			
	BMD lumbar spine, total hip and femoral neck, BMD Wrist	s-PINP, s-CTX	vBMD	
Visit 3 / Baseline	≤1	$\leq 1$	≤ 1	
Visit 4 / Month 1		2—60		
Visit 5 / Month 3	2—120	61—120		
Visit 6 / Month 6	121—270	121—270		
Visit 7 / Month 9				
Visit 8 / Month 12	≥ 271	≥271	≥2	

*Study BA058-05-019 SAP* 

It is possible that more than 1 assessment for a parameter may be obtained within the same analysis visit window. In such circumstances, the assessment with the date closest to the ideal visit day will be used. In the event that 2 assessments are equidistant to the ideal visit day, the later of the assessments will be used.

The analysis visit window convention will not be applied to the data listings. The data listings will display all data as collected with the corresponding nominal visit.

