6.6.2. Quantitative Computed Tomography

A subset of subjects at a selected number of study sites will have volumetric BMD (vBMD) measurements taken via QCT of the hip on Day 1 (Visit 3) and Month 12 (Visit 8).

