## **1.2.5 Efficacy and Safety Parameters**

#### **Efficacy Parameters**

The primary efficacy endpoint is:

• Percent change from baseline in lumbar spine bone mineral density (BMD) at 12 months.

The key secondary efficacy endpoints are:

- Percent change from baseline in total hip BMD at 12 months
- Percent change from baseline in femoral neck BMD at 12 months

Additional secondary efficacy endpoints are:

- Percent change from baseline in:
  - Lumbar spine BMD at 3 and 6 months
  - Total hip BMD at 3 and 6 months
  - Femoral neck BMD at 3 and 6 months
  - Ultra-distal radius BMD at 3, 6 and 12 months
  - Distal one-third radius BMD at 3, 6 and 12 months
- Log ratio of post-baseline over baseline in:
  - Serum procollagen type I N-terminal propeptide (s-PINP) at 1, 3, 6 and 12 months
  - Serum carboxy terminal cross linking telopeptide of type I collagen (s-CTX) at 1, 3, 6 and 12 months.
- Proportion of subjects experiencing BMD gains from baseline of >0%, >3%, and >6% at the lumbar spine, femoral neck, and total hip at 3, 6, and 12 months
- Incidence of new clinical fractures at 12 months
- Proportion of subjects converting from the categories of Osteoporosis to Osteopenia and Normal at end of treatment, where:
  - Osteoporosis is defined as lumbar spine or total hip BMD T-score  $\leq$  -2.5,
  - Osteopenia is defined as:
    - $\circ$  lumbar spine > 2.5 and total hip BMD T-score > -2.5 and < -1.0, or
    - $\circ$  lumbar spine > 2.5 and < 1.0 and total hip BMD T-score > -2.5,
  - Normal is defined as lumbar spine and total hip BMD T-score  $\geq$  -1.0.
- The percent change in total hip and femoral neck volumetric BMD as measured by quantitative CT (QCT) from baseline to 12 months. QCT will be performed in a subset of subjects at a selected number of study sites.

For those subjects who consent to PK sample collection, the PK endpoints are:

- The plasma concentration of abaloparatide based on sparse PK sampling at the following visits:
  - Month 6: post-dose PK samples collected 45 minutes (±15 minutes) and 2.5 hours (±0.5 hour) after abaloparatide-SC injection
  - Month 9: post-dose PK samples collected 20 minutes (±10 minutes) and 4 hours (±0.5 hour) after abaloparatide-SC injection

- Month 12: a pre-dose sample and a post-dose sample collected 1.5 hours (±0.5 hour) after abaloparatide-SC injection

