Analysis of the time to new clinical fracture during the study will be performed for exploratory purposes. Duration in days from the date of randomization to the first incidence of clinical fracture will be derived. The crude incidence rates of new clinical fracture, Kaplan-Meier estimates of the incidence rate at Month 12, hazard ratio (95% CI) based on a Cox proportional hazard model, Kaplan-Meier curves, and p-values from the log-rank test for the comparison of the treatment groups will be generated using the ITT and PP populations for this time-to-event variable. If a subject does not experience any clinical fracture over the 12 months of treatment plus the 30-day follow-up, this subject will be censored at the last known day in the study up to the follow-up visit.

The number and percentage of subjects for whom disease status has changed from osteoporosis at baseline to osteopenia or to normal (Refer to Section 4.3.2 for the definitions of osteoporosis, osteopenia, and normal), or no change at end of treatment will be tabulated; and will be analyzed using the Cochran-Mantel-Haenszel (CMH) test stratified by baseline disease status for the ITT population. No imputation of missing BMD data will be implemented.

The percent change from baseline in total hip and femoral neck volumetric BMD (vBMD) at Month 12, as measured by quantitative computed tomography (QCT), will be analyzed using an ANCOVA model with fixed effects of treatment and DXA instrument manufacturer, and with the relevant vBMD baseline value as covariate for the ITT population. No imputation of missing vBMD data will be implemented.

Study BA058-05-019 SAP

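### SAP Table 4 counts any QCT scan from Day 2 onward as Month 12, so an early-termination scan can be reported as a 12-month vBMD result; the effect is small and its direction depends on the comparator

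*SAP*

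**What the plan says.** The SAP (1.2.5, repeated in 4.3.2) defines the endpoint as "The percent change in total hip and femoral neck volumetric BMD as measured by quantitative CT (QCT) from baseline to 12 months". It is an additional secondary endpoint, measured in a subset of men at selected sites and outside the fixed testing sequence.

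QCT is scheduled twice: Day 1 and Visit 8 (Protocol 6.6.2). Visit 8 is the combined Month 12/Early Termination visit, and its procedure list includes the hip QCT (Protocol 6.2.13). Men who withdraw are encouraged to complete that visit promptly (Protocol 4.3.2).

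SAP 3.12 introduces Table 4 by saying that "analysis visit windows are defined below for the analyses of BMD, vBMD, and serum markers of bone metabolism (PINP and CTX) data". In the row "Visit 8 / Month 12", areal BMD and bone markers must be at Day 271 or later, while vBMD needs only Day 2 or later. If a window holds several scans, "the assessment with the date closest to the ideal visit day will be used". SAP 4.3 makes these windows the primary analysis for BMD-related endpoints and the nominal visit supportive.

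SAP 4.3.2 analyses vBMD at Month 12 with "an ANCOVA model with fixed effects of treatment and DXA instrument manufacturer, and with the relevant vBMD baseline value as covariate", and adds: "No imputation of missing vBMD data will be implemented".

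**The concern.** The window and the endpoint definition disagree. An early-termination scan at, say, Day 150 would be analysed as a 12-month measurement. The closest-day rule does not help, because it chooses between scans and this man has only one. SAP Table 3 limits how late a QCT may be collected during the pandemic but sets no earliest day.

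The same man's DXA is handled differently. A Day 150 DXA falls in the Month 6 window (Days 121 to 270), and his Month 12 areal hip BMD is wash-out imputed. The vBMD and areal hip results will be read side by side, yet they treat leavers by different rules, and the SAP does not say so.

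At stake are the accuracy of the *Month 12* label and the comparability of two hip results. A smaller, separate matter is that DXA instrument manufacturer does not describe a CT measurement.

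**Working it through.** **The plan's own figure.** This is a window bound, so there is no formula to reproduce. For vBMD the Month 12 window opens 360 − 2 = 358 days before the ideal day; for areal BMD, 360 − 271 = 89 days. The difference is 269 days.

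**Inputs.** From the documents: 10% drop-out (SAP 3.1, whole trial); ideal Day 360; the Day 271 bound; the per-protocol exclusion of men with under 90 days' exposure (SAP Appendix A, B.2). Assumed, because the documents give no figure: the 10% applies to the QCT subset; drop-out is uniform over 360 days and equal by arm; the scan is taken when the man stops; uptake u of that scan (QCT and DXA alike) is 25%, 50% or 100%; gain is linear in time, with square root of time as a front-loaded alternative. Low uptake is plausible, since SAP 4.3.1 says the study does not systematically collect data after early discontinuation.

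**Step 1: against men scanned at Month 12.** Leavers before Day 271 are 10% × 270/360 = 7.5% of men.

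- ITT: early-only share f = 0.075u/(0.90 + 0.10u). Mean early scan is Day 135, so the fraction of gain reached is r = 135/360 = 0.375 (linear) or (2/3)√0.75 = 0.577 (square root). Shortfall = f(1 − r).
- Per-protocol: early-only scans now run from about Day 90 to Day 270, so f = 0.05u/(0.90 + 0.075u), with r = 180/360 = 0.50 (linear) or (2/3)(0.75^1.5 − 0.25^1.5)/0.5 = 0.699 (square root).

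| Uptake u | 25% | 50% | 100% |
|---|---|---|---|
| ITT, early-only share f | 2.03% | 3.95% | 7.50% |
| ITT shortfall, linear | 1.27% | 2.47% | 4.69% |
| ITT shortfall, square root | 0.86% | 1.67% | 3.17% |
| PP, early-only share f | 1.36% | 2.67% | 5.13% |
| PP shortfall, linear | 0.68% | 1.33% | 2.56% |
| PP shortfall, square root | 0.41% | 0.80% | 1.54% |

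**Step 2: against the wash-out-imputed DXA hip result.** Take linear gain and zero treatment effect for an imputed leaver. Leavers from Day 271 are 2.5% of men; if scanned, they have reached on average 315/360 = 0.875 of the gain. As a fraction of the full Day 360 effect:

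- DXA: 0.90 + 0.025u × 0.875, over all men.
- vBMD as planned: (0.90 + 0.025u × 0.875 + 0.075u × 0.375)/(0.90 + 0.10u).
- vBMD at Day 271 or later only: (0.90 + 0.025u × 0.875)/(0.90 + 0.025u).

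| Percent below the full effect, by uptake | 25% | 50% | 100% |
|---|---|---|---|
| DXA, wash-out imputed | 9.45% | 8.91% | 7.81% |
| vBMD as planned | 1.35% | 2.63% | 5.00% |
| vBMD, Day 271 or later only | 0.09% | 0.17% | 0.34% |

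The gap between DXA and planned vBMD runs from 9.45 − 1.35 = 8.1 points to 7.81 − 5.00 = 2.8 points. It comes from not imputing vBMD. Restricting to Day 271 or later would widen it.

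**Step 3: the DXA term.** One or two extra degrees of freedom raise the two-sided 5% critical t by 0.18% to 0.38% in an assumed subset of 30, and by 0.01% to 0.03% in one of 100.

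**The case against.** The strongest reply is that the open window is deliberate. QCT has one post-baseline time point, so Day 1 or earlier and Day 2 or later simply divide baseline from follow-up, and the windows are declared in SAP Section 5. That is a fair explanation of the cell. It leaves the label wrong: an analysis of the last available scan is an end-of-treatment analysis, and Section 5 made exactly that change of wording for T-score conversion.

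Other planned work helps in part:

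- **Listings.** They show all data with relative study day (SAP 3.2, 3.11, 3.12), so early-only scans can be identified. A reader might infer that they would be hidden; they would not. But no planned table counts them by arm.
- **DXA LOCF analyses.** Those for total hip and femoral neck (SAP 4.3.1, 4.3.2) carry a leaver's last DXA forward, a nearer like-for-like comparison for vBMD. The SAP does not point to it.
- **Nominal-visit analysis.** This keeps the early scans, because Month 12 and Early Termination are one nominal visit.
- **Per-protocol repeat.** Protocol 8.4.3 plans it for secondary endpoints, though the SAP's vBMD paragraph names only ITT. Scans from about Day 90 to Day 270 stay in.
- **Table 5 (Month 12 as Days 271 to 390).** SAP 4.3.2 extends the primary endpoint's analyses to additional BMD parameters, so Table 5 might be meant to cover vBMD. But it is titled for DXA, its analyses are wash-out imputed, and vBMD has its own un-imputed model. The text leaves this open.

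It is also fair that every input to the size except the drop-out rate is assumed.

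**Conclusion.** The point holds and is minor. The rule in Table 4 conflicts with the 12-month endpoint definition, and no planned analysis clearly resolves it.

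On the stated assumptions, 2.0% to 7.5% of analysed men would have only an early scan, and the ITT effect would be about 1.3% to 4.7% smaller than in men scanned at Month 12. It would be less under front-loaded gain or in the per-protocol repeat. Confidence is high in the reading of the table and much lower in the size, since subset size, uptake, timing, shape of gain and balance by arm are not documented.

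Three stronger readings are not supported. First, that the planned result is simply conservative: this is true only against men scanned near Month 12, whereas beside the wash-out-imputed DXA hip result vBMD is the less attenuated of the two. Second, that the Day 2 window causes that gap: it comes from not imputing vBMD, and the early scans narrow it. Third, that the trial's main conclusions are affected: no primary or key secondary result changes.

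The DXA manufacturer term follows the protocol's reference to a similar ANCOVA (8.4.3). Under randomisation it should not by itself bias the comparison, and its numerical effect is negligible.

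**What to change.** 1. Keep all scans, but label the vBMD analysis *end of treatment*, in line with the T-score change in SAP Section 5.
2. Add a sensitivity analysis limited to scans at Day 271 or later, described as close to a completer analysis. It checks the time-point label; it does not bring vBMD closer to the DXA result.
3. Tabulate the number and timing of early-only scans by arm.
4. State that leavers are handled differently from the wash-out-imputed DXA hip analysis, and that the planned DXA LOCF analysis is the nearer comparison.
5. State whether the extension of the primary endpoint's analyses, and Table 5 with it, applies to vBMD.
6. Separately, remove DXA instrument manufacturer from the vBMD ANCOVA.

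The cost is a few short SAP edits, one sensitivity analysis and one table. The downside is that the main vBMD result is no longer described as a pure 12-month effect.

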## 3.13 Interim Efficacy Analyses

No interim analysis for efficacy is planned for this study.

## 4 STUDY ANALYSES

#### 4.1 Subject Disposition

Subject disposition will be tabulated by treatment group including the number screened, the number randomized, the number treated, the number in each analysis population, the number who completed the study, the number who discontinued from the study treatment together with the primary reason for discontinuation, and the number who discontinued from the study together with the primary reason for discontinuation as recorded in the eCRF. The number of subjects excluded from the PP population together with the exclusion reasons will also be summarized.

A Kaplan-Meier plot of the time from randomization to withdrawal from study will be presented by treatment. Subjects who complete the study will be censored at the date of their study completion.

The total number of subjects randomized will be tabulated by region (North America, Europe), country, study site, and treatment group.

Subject disposition data will be carefully reviewed with respect to the impact of the COVID-19 pandemic on study conduct. Significant protocol deviations and study/treatment discontinuation related to the COVID-19 pandemic will be identified during the study. A summary of subject disposition by subject's randomization date relative to COVID-19 pandemic onset (subjects randomized prior to 01 March 2020 vs subjects randomized on or after 01 March 2020) will be presented. A summary of subject disposition based on subject's study status relative to COVID-19 pandemic onset (subjects who completed or withdrew from the study before 01 March 2020 vs subjects who completed or withdrew from the study before 01 March 2020 vs subjects who completed or withdrew from the study before 01 March 2020 vs subjects who completed or withdrew from the study before 01 March 2020 vs subjects who completed or withdrew from the study before 01 March 2020 vs subjects who completed or withdrew from the study before 01 March 2020 vs subjects who completed or withdrew from the study before 01 March 2020 vs subjects who completed or withdrew from the study before 01 March 2020 vs subjects who completed or withdrew from the study before 01 March 2020 vs subjects who completed or withdrew from the study on or after 01 March 2020) will also be presented. The number (%) of subjects with assessments impacted by COVID-19 pandemic as recorded on the COVID-19 Impact Log eCRF page will be summarized by visit and the following categories:

- Altered Protocol Assessment/Procedure
- Discontinuation
- IP Missed/Modified
- Missing Data
- Missed Visit
- Out of Window Visit
- Remote /Virtual Visit
- Assessment Not Done
- Other

A listing of subjects with assessments impacted by COVID-19 pandemic as indicated on the COVID-19 Impact Log eCRF page will be provided. The listing will include subject ID, age, race, site, visit, CRF form used, impact category, and comment.

A by-subject data listing of study completion information, including the primary reasons for premature study withdrawal as recorded in the eCRF, will be presented. A by-subject data listing of subject excluded from PP population and the reasons for exclusion will also be presented.

A summary of screening failures and listings of inclusion/exclusion criteria responses for screening failure subjects will also be presented.

## 4.2 Demographics and Baseline Characteristics

Demographic and baseline characteristics will be summarized and presented by treatment group and overall. Age will be calculated as of the date the subject provided signed informed consent for this study. Age, age group (<65, 65-<75,  $\geq$ 75), height, weight, body mass index (BMI), and BMI group (BMI < 25, 25  $\leq$  BMI < 30, BMI  $\geq$  30) will be summarized using descriptive statistics (number of subjects, mean, SD, median, interquartile range, minimum and maximum). The number of subjects in each ethnicity and race category will also be presented. Subjects who report more than one race category will be counted under the race category "Multiple". The usage of alcohol, tobacco, and other substances at baseline will be summarized by treatment group.

The number and percentage of subjects with the following fracture history will be summarized:

- Prior clinical fracture: Subjects with a record in medical history with "fracture" in the preferred term.
- Prevalent vertebral fracture: Subjects with any vertebral fracture with a score > 0.
- Prior fracture: Subjects with a prevalent vertebral fracture and / or a prior clinical fracture
- Prior clinical vertebral fracture: Subjects with a record in medical history with "vertebral fracture" or "spinal fracture" in the preferred term
- Prior vertebral fracture: Subjects with a prior clinical vertebral fracture or a prevalent vertebral fracture.

Baseline values for BMD measurements and biomarker parameters including lumbar spine BMD T-score and T-score group ( $\leq -2.5$ ,  $\geq -2.5$ ), total hip BMD T-score and T-score group ( $\leq -2.5$ ,  $\geq -2.5$ ), femoral neck BMD T-score and T-score group ( $\leq -2.5$ ,  $\geq -2.5$ ), s-PINP and s-PINP group (tertile values), s-CTX, total testosterone level and total testosterone level group ( $\leq 9.36$  nmol/L,  $\geq 9.36$  nmol/L), and estradiol level and estradiol level group ( $\leq 73.4$  pmol/L,  $\geq 73.4$  pmol/L) will also be summarized for each treatment group and overall.

BMD measurements via Quantitative Computed Tomography (QCT) will be collected in a subset of subjects at a selected number of centers. The summary of demographics and baseline characteristics will be repeated for this subset of subjects.

Medical history will be presented by MedDRA system organ class (SOC), preferred term (PT), and treatment group, summarizing the proportion of subjects in each treatment group who have a condition noted.

Results from the baseline physical examination will be summarized by body system as recorded in the eCRF and treatment group.

All analyses described in this section will be performed on the ITT population, and repeated for the Safety and PP populations.

All analyses described in this section will also be repeated for the Antibody population. The presentation of these analyses will be based on subjects' ADA status and presence of neutralizing

antibody (NAb) during the study with columns for ADA-, ADA+/NAb+, ADA+/NAb-, All ADA+, and Overall.

Additionally, demographics data and baseline characteristics will be tabulated by all subgroups listed in Section 3.8 using the ITT population. To address the effect of the COVID-19 pandemic, summaries of demographic data and baseline characteristics by subject's randomization date relative to COVID-19 pandemic onset (subjects randomized prior to 01 March 2020 vs subjects randomized on or after 01 March 2020) will be presented. Summaries of demographic data and baseline characteristics based on subject's study status relative to COVID-19 pandemic onset (subjects who completed or withdrew from the study before 01 March 2020 vs subjects who completed or withdrew from the study on or after 01 March 2020) will also be presented.

Demographics including gender, race, ethnicity, age, and country for screen failure subjects will also be summarized descriptively.

All subject data collected for demographics and baseline characteristics will be presented by treatment, study site, and subject number in data listings.

